12.2.3.2 Statistical considerations for patient reported outcomes

Statistical analyses

Primary endpoint – Fatigue

For the primary hypothesis, the composite fatigue score (FACIT-Fatigue questionnaire) measured at 6 and 12 months after randomisation will be compared between the two treatment arms using analysis of covariance (ANCOVA) with adjustment for the corresponding baseline measurement. Separate analyses will be done for patients who have received prior neoadjuvant chemotherapy and patients who have received standard post-surgical adjuvant chemotherapy. Separate analyses are preferable because the timing of chemotherapy is expected to impact the fatigue outcome directly. Each comparison will be performed at the significance level of 0.05. No multiple comparisons adjustment will be employed since these outcomes evaluate the toxicity of the study treatment.

To further assess the effect of olaparib on fatigue over time (study treatment period and the year following) the composite fatigue score (FACIT-Fatigue questionnaire) measured at 6, 12, 18 and 24 months after randomisation will be compared between the two treatment arms using a mixed model for repeated measures (MMRM) analysis of all of the post baseline scores. The model will include treatment, time and treatment by time interaction as explanatory variables and baseline score and baseline by time interaction as covariates. The treatment by visit interaction will remain in the model regardless of significance. The adjusted mean change from baseline estimates for each treatment arm, difference in the adjusted mean change from baseline estimates between the arms and corresponding confidence intervals will be presented by time point. Plots of the adjusted means changes over time will also be presented.

Secondary PRO endpoints

A secondary analysis based on GI symptoms (nausea, vomiting and diarrhea) over time from the EORTC QLQ-C30 scale will be performed using the same MMRM model described above. The adjusted mean change from baseline estimates for each treatment arm, difference in the adjusted mean change from baseline estimates between the arms and corresponding confidence intervals will be presented by visit. Plots of the adjusted means changes over time will also be presented for nausea, vomiting and diarrhea.

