A certain amount of missing data is expected. If data for individual items are missing, imputation will be done as follows: if less than 50% of the subscale items were missing (e.g. at most 2 out of 5 items, etc), the subscale score based on the non-missing items will be divided by the number of non-missing items and multiplied by the total number of items on the subscale. If at least 50% of the items are missing, that subscale will be treated as missing (not evaluable). If the scale is a single-item measure, a missing value will automatically be defined as 'Non-Evaluable'. The information from patients with missing data will be reviewed in order to determine whether data analytic procedures are likely to be biased. Patients with missing data will be reviewed for imbalances in factors such as trial arm, treatment adherence, institution, and reason for non-adherence. When QOL data are missing at a particular time point, data from prior time points will be reviewed in order to investigate whether missing status was preceded by a significant change in QOL scores. In addition, we will investigate whether missing item status is related to other scores on the same questionnaire. If no missing data mechanism can be detected following this review, the data will be analysed assuming the data are missing at random. If, on the other hand, a missing data mechanism appears to be present, we will undertake to develop an appropriate analytic strategy to control for the potential bias and, if possible, to impute the missing values. We will also present sensitivity analyses based on varying assumptions about the missing-data mechanism.

Full details on the analysis and derivation of PRO endpoints will be provided in the statistical analysis plan (SAP).

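### The missing-PRO review in Section 12.2.3.2 tests MCAR and cannot support or refute MAR, and the baseline-only ANCOVA for fatigue is biased at 12 months if missingness follows the 6-month score differently by arm

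*Protocol*

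**What the plan says.** All of this stands in Protocol Section 12.2.3.2.

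- **Primary fatigue model.** FACIT-Fatigue scores at 6 and 12 months "will be compared between the two treatment arms using analysis of covariance (ANCOVA) with adjustment for the corresponding baseline measurement", separately for neoadjuvant and adjuvant patients.
- **Longitudinal model.** An MMRM of all post-baseline scores (6, 12, 18 and 24 months) is specified to assess fatigue further over time.
- **The review of missing data** has three parts: "Patients with missing data will be reviewed for imbalances in factors such as trial arm, treatment adherence, institution, and reason for non-adherence"; "data from prior time points will be reviewed in order to investigate whether missing status was preceded by a significant change in QOL scores"; and "we will investigate whether missing item status is related to other scores on the same questionnaire".
- **If nothing is found:** "If no missing data mechanism can be detected following this review, the data will be analysed assuming the data are missing at random".
- **If something is found:** "we will undertake to develop an appropriate analytic strategy to control for the potential bias and, if possible, to impute the missing values".
- **In either case:** "We will also present sensitivity analyses based on varying assumptions about the missing-data mechanism".

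Further PRO detail is left to the SAP, which is not at hand.

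**The concern.** The review is used to decide whether MAR may be assumed, but every quantity it examines is observed. Under MAR, missingness is allowed to depend on observed data, so a positive finding is compatible with MAR. Under not-MAR, missingness depends on the unseen score, which the review cannot reach except through that score's correlation with what was seen. The trigger therefore separates MCAR from everything else. It does not separate MAR from not-MAR.

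There is a second problem. The primary model needs more than MAR. A 12-month ANCOVA on patients with a 12-month score, adjusted only for arm and baseline, is valid if missingness depends on arm and baseline alone. It discards the 6-month score of a patient who then misses month 12. The MMRM in the same section uses it.

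Fatigue is the primary PRO outcome, the protocol hypothesises that it will be worse on olaparib, and 20% missing data are planned for at 12 months. Loss related to fatigue that differs by arm is plausible. At stake are the size of the reported fatigue difference and whether its analysis is fixed before the data are seen.

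**Working it through.** **1. The plan's own figures reproduce.** Inputs from the sample size paragraph of Section 12.2.3.2: 1800 patients, 15% hormone-receptor positive (270) and so 1530 triple negative; neoadjuvant shares 25% and 50%; 95% complete the instrument; 20% missing at 12 months; difference 3; SD 10.9; alpha 0.05 (taken as two-sided).

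- Neoadjuvant: 1530×0.50 + 270×0.25 = 832.5 randomised; ×0.95 = 790.9 completing the instrument (about 791); ×0.80 = 632.7. Stated: 633.
- Adjuvant: (1530×0.50 + 270×0.75)×0.95×0.80 = 735.3. Stated: 735.
- Power = Φ(3/SE − 1.96), with SE = 10.9×√(4/n). For n = 633, SE = 0.867 and power is 93.3%. For n = 735, SE = 0.804 and power is 96.2%. Stated: 93% and 96%.

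These figures are not in dispute.

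**2. What the review can tell.** Let R indicate a missing score.

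| Mechanism | R depends on | Does the review find a link? | MAR analysis valid? |
|---|---|---|---|
| MCAR | nothing | only by chance | yes |
| MAR | observed scores and factors | yes, if strong enough | yes |
| Not MAR, unseen score correlated with earlier ones | the unseen score | usually | no |
| Not MAR, no trace in observed data | the unpredicted part of the unseen score | only by chance | no |

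A finding is shared by the second and third rows, and no finding by the first and fourth. Each pair contains one case where MAR holds and one where it does not, so neither outcome settles MAR.

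**3. Size, by simulation.** There were 791 patients with baseline, 6- and 12-month scores, normal with SD 10.9, a true 3-point difference at both visits, and about 20% missing at 12 months. Correlations were 0.5 (baseline with 6 months), 0.45 (baseline with 12) and 0.7 (6 with 12). The review was represented by a 5% test of the 6-month score, centred within arm, in patients with and without a 12-month score. The MAR-likelihood estimate uses the 6-month score, as an MMRM does. Correlations, slopes and intercepts are assumptions, not protocol figures. The slope is the change in the log odds of missingness per point. Flag rates and estimates come from repeat runs that differ by a few hundredths of a point.

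| Missingness at 12 months | Review flags | ANCOVA | MAR-likelihood |
|---|---|---|---|
| 6-month score, olaparib arm only, slope -0.02 | about 21% | 2.81 | about 3.0 |
| same, slope -0.04 | about 67% | 2.55 | about 3.0 |
| same, slope -0.08 | over 99% | 1.99 | about 3.0 |
| 6-month score, both arms, slope -0.08 | about 100% | 2.84 to 2.90 | about 3.0 |
| 12-month score itself, olaparib arm, slope -0.08 | 93% | biased | biased |
| unpredicted part of the 12-month score, olaparib arm, slope -0.15 | 5% | 1.42 | 1.41 |

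At the steepest one-arm slope, ANCOVA power is about 72%. With no true difference, the same mechanism gives ANCOVA a false difference of about 0.9 points and about 20% rejection at a nominal 5%; the MAR-likelihood bias is 0.0.

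**4. A second set of assumptions gives the same pattern.** With correlations 0.6, 0.5 and 0.6 and slopes steeper on olaparib than on placebo, the review flagged 5% under MCAR. It flagged 100% under MAR through the 6-month score (ANCOVA bias 0.9, MAR-likelihood bias 0.0) and 100% when missingness followed the 12-month score itself (MAR-likelihood bias 1.9). When missingness followed only the unpredicted part, in opposite directions in the two arms, it flagged 4% (bias 3.0 for both models).

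**The case against.** A reader might infer that the rule abandons a MAR analysis whenever MAR holds and keeps it whenever missingness is informative. The documents do not support that, for three reasons.

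- After a finding the text leaves the strategy open. Conditioning on observed predictors or imputing can itself be a MAR method, and neither ANCOVA nor MMRM is made conditional on the review. What stands against the plan is that this strategy is undefined until the data have been seen.
- Informative missingness usually does leave a trace. When it follows the 12-month score itself, the review flags it in 93% to 100% of simulated trials. False reassurance is confined to missingness unrelated to anything observed.
- Sensitivity analyses under varying assumptions are promised whatever the review finds. They limit the harm, though they do not change which analysis is primary. Their detail belongs to the SAP and its absence here is no fault.

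Other points also carry weight. Section 6.5.3 keeps patients who stop drug for reasons other than recurrence or a second cancer on the PRO schedule and foresees completion by phone or mail, which limits fatigue-related loss. The same section ends PRO assessment for patients who never start study drug, so wherever such patients exist, a link between missingness and adherence, one of the review's triggers, is built in. No figure in the protocol supports a strong slope in one arm only; at -0.02 the ANCOVA loses about 0.2 points. The MMRM contrasts at 6 and 12 months will be produced anyway. Finally, PROs are secondary and lie outside the multiple testing procedure of Section 12.2.5.

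These arguments reduce the stakes. They do not make the trigger correct.

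**Conclusion.** The point holds in limited form. The decision rule is written into the protocol and its logic is wrong: a review of observed data tests MCAR and can neither support nor refute MAR. Two consequences follow. The primary PRO analysis may be settled after seeing the data in just those cases where a MAR analysis would be valid, and an empty review gives no assurance against informative missingness that leaves no trace.

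Separately, the ANCOVA is biased at 12 months if missingness follows the 6-month score and differs by arm. Over the assumed one-arm slopes the loss is 3.0 − 2.81 = 0.19 to 3.0 − 1.99 = 1.01 points of a 3-point difference. It is 0.10 to 0.16 points when both arms share the mechanism. These sizes rest on assumed correlations and slopes and show a range; they do not predict what this trial will see. Nothing here touches the stated PRO sample size or power, or the IDFS, DDFS and OS analyses.

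**What to change.** Amend Section 12.2.3.2 as follows.

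1. State MAR in advance as the primary working assumption for the PRO analyses, whatever the review shows.
2. Read the 6- and 12-month FACIT-Fatigue comparisons from the MMRM already specified, fitted within the neoadjuvant and adjuvant groups as planned for the primary comparison. Keep the per-visit ANCOVA as supportive.
3. Keep the review of missingness as description only, and delete the sentences that make the analysis depend on it.
4. Include at least one not-MAR analysis among the promised sensitivity analyses, for example a shift applied to missing olaparib-arm scores, ranging up to the 3-point relevant difference. The detail can go in the SAP.

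The cost is wording. The model and the sensitivity analyses are already planned and no further data are needed. The small downside is that the primary PRO result then relies on the covariance structure of the MMRM.

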12.2.3.3 Pharmacokinetic analysis

The plasma concentration-time data will be analysed by non-linear mixed effects modelling in order to evaluate the pharmacokinetic characteristics of olaparib, quantify variability in the pharmacokinetics, identify demographic or pathophysiological covariates which may explain the observed variability and explore exposure-response relationships.

The olaparib plasma concentration data obtained from the samples collected in this study will be included in the listings of the CSR but these data will be pooled with data from other studies in order to perform a population PK analysis. The results of this analysis will be reported in a separate population PK report.

12.2.4 Analysis of exploratory endpoints

Adjusted OS (assessing potential impact of subsequent PARP inhibitors or other active therapies)

Exploratory analyses of OS that make an attempt to adjust for any potential impact of the control arm receiving subsequent PARP inhibitors (including patients taking part in PARP trials where exact treatment allocation may not be known) may be performed if an appropriate proportion of patients on the control arm switch to PARP inhibitors and sufficient data is collected to support such analyses (Note platinum therapies may also be taken into consideration if important imbalances are observed between the treatment arms). Methods such as Rank Preserving Structural Failure Time (RPSFT) ([Robins et al 1991](#)), and other methods in development will be explored. The decision on whether to perform these adjusted analyses and final choice of methods will be based on a blinded review of the data and the plausibility of the underlying assumptions as well as the completeness of the data collection on subsequent therapy use. Baseline and time-dependent characteristics will be explored, and summaries of baseline characteristics will be summarised for placebo patients, splitting between those that have and haven't switched to PARP inhibitors at the time of the analyses. Further detail will be provided in the SAP and Payer Analysis Plan. Note: these analyses are intended to support reimbursement applications, where applicable.

Biomarkers

Biomarker data will be summarised descriptively using tables and plots. If the data are available at the time of developing the CSR then the biomarker data will be included in the CSR. Otherwise the biomarker data will be reported in a separate addendum to the CSR (if applicable). Further details on the data summaries and plots for the biomarker data will be provided in the SAP or biomarker analysis plan.

All randomised patients were required to have two blood samples taken in relation to *BRCA* testing. One sample will be used to confirm *BRCA* status for the study patients (using the central Myriad test) and the other will be used to support diagnostic development.

All patients will have their *BRCA* status confirmed via the central test and the results will be summarised, highlighting any patient for whom the central test does not confirm a *BRCA* mutation (i.e. patients who may have entered via a positive local test not confirmed by the central test).

There is expected to be very few patients for whom the *gBRCA* central test result would differ from the local result, however if there are patients in this situation then an analysis of IDFS, DDFS, and OS will be performed which will include only those patients with confirmation of a *gBRCA* mutation by the central Myriad test.

12.2.5 Multiplicity strategy for primary and key secondary endpoints

[figure not shown]
The primary endpoint of the study is IDFS. However, key secondary endpoints will be OS and DDFS.

In order to describe the nature of the benefits of olaparib treatment IDFS, DDFS and OS will be tested at a 2-sided significance level of 5%.

However, in addition, in order to strongly control the overall type I error at 2.5% 1-sided, a multiple testing procedure (MTP) will be employed across the primary endpoint and all key secondary endpoints intended for label claims (DDFS and OS). The MTP will account for any interim analyses on IDFS, DDFS and OS and also planned further analyses post the primary IDFS analysis data cut off.

A hierarchical testing strategy will be employed where IDFS is tested first using the full test mass (i.e. full 2.5%, 1-sided alpha), then DDFS and OS will be tested if IDFS is significant based on a weighted proportion of the test mass (2% for DDFS and 0.5% for OS, 1-sided) which can be recycled to secondary endpoints not yet rejected. Testing stops when the entire test mass is allocated to non-rejected endpoints.

Figure 3 Multiple testing procedure

IDFS is planned to be analysed at the interim and the final analysis (see [Section 12.2.6](#) for further details). If IDFS is significant at the interim based on the ITT population then secondary endpoints will be formally tested at the interim based on the MTP outlined above. To account for multiple analyses on each endpoint a separate alpha spending function will be applied to each

endpoint ([Glimm et al 2010](#)). Further analyses of DDFS and OS with more mature follow up may be required for which some alpha will be reserved for significance testing.

12.2.6 Interim analysis

A superiority interim analysis of IDFS will occur when half the events needed for at least 90% power (165 events) have been observed from the first 50% of patients recruited (i.e. from first 900 patients) providing a cohort of patients with a similar level of maturity that is planned for the final analysis. Based on the database at time of amendment, the interim analysis is predicted to be October 2019 (80% CI: March 2019 to August 2020). The predictions will be tracked and monitored as more patients are enrolled in the study and additional data is added to the database. Two populations will be analysed at the interim analysis based on the analysis methods described in [Section 12.2.1](#) for IDFS

1. Primary: ITT population (all patients randomised, estimated 254 events [80% CI: 226 to 289])
2. Supportive: Mature cohort population (first 900 patients randomised, 165 events anticipated)

The inclusion of a mature cohort population at the interim is to provide confidence that any observed treatment effect from the interim ITT population is maintained with longer-term follow-up. It is anticipated, based on the assumed recruitment and event rate that the interim analysis will occur approximately 5.3 years after the first patient is randomised and that all patients will have been randomised. At the time of the interim analysis, median time at risk per patient is expected to be 27 months in the ITT set, and 34 months in the mature cohort. The critical HR value at the interim analysis is 0.701.

Evidence of superiority for IDFS would only be determined at the interim if the results from both analysis populations provide evidence of a sustainable clinically relevant treatment effect for IDFS. More specifically, as a minimum the result in the ITT population would need to have met the statistical threshold defined below. Having met the statistical threshold in the ITT population, the result in the mature cohort (i.e. HR) would need to be of a similar magnitude such that the IDMC would consider it supportive of the ITT result and therefore have added confidence in the result in the ITT population. Statistical significance is not required for the mature cohort population. This analysis will be regarded as supportive, based on a cohort of patients with longer term follow-up, to aid interpretation of the result in the ITT population based on interim data. Other outcome measures such as 3 year IDFS rate will also be presented to aid the interpretation of the HRs (particularly in the case where the assumption of proportional hazards may not hold). KM plots will also be produced for IDFS.

The test mass alpha for IDFS (1 sided 2.5%) will be split between the final and the interim analysis using a bespoke spending function where a fixed significance level will be assigned at the interim and the remaining significance level assigned to the final analysis, taking account of correlation ([Stone 2010](#)). A 2-sided significance level of 0.005 will be assigned to the interim analysis so that a highly significant and clinically relevant result will need to be observed to declare superiority on IDFS. As an illustration, if 70% of the total required 330 IDFS events

have occurred in the ITT population at the interim then the observed HR would need to be < 0.7 for superiority to be declared. The HR in the mature cohort would need to be supportive of the ITT result. More detail around the criteria required for the mature cohort will be provided in the IDMC charter or SAP.

If the null hypothesis for IDFS is rejected at the interim for the ITT population then secondary endpoints (DDFS and OS) will be tested based on the MTP procedure outlined in [Section 12.2.5](#) using the significance levels provided in [Table 15](#). If IDFS is not significant at the interim, DDFS and OS will not be tested at the IDFS interim and the significance level allocated to the IDFS interim for DDFS and OS will not be allocated to later timepoints.

Similar to IDFS, a bespoke spending function will be applied to the secondary endpoints OS and DDFS where a fixed significance level will be assigned to each analysis time point and the remaining significance level assigned to the final analysis time point controlling the overall type 1 error at the pre-specified alpha amount ([Stone 2010](#)). Provided the last analysis is known in advance of the penultimate one then the remaining alpha can be split to ensure that some alpha is always reserved for the final analysis. This approach allows flexibility in the number of analyses while appropriately controlling the overall type 1 error. Three analyses are planned for DDFS and four for OS for which some alpha will be reserved for significance testing. If additional analyses are required beyond the planned analyses and some alpha is still available for testing then any remaining alpha can be further split to strongly control the type 1 error (based on process described above). If no alpha remains then the additional analyses will be considered supportive updates of the already conducted analyses.

Given the split in alpha between DDFS and OS, if OS is significant based on the assigned significance level then the alpha assigned to OS will be recycled to DDFS and split across the planned analyses (and vice versa if DDFS is significant alpha for DDFS will be recycled to OS and split across analyses). The recycled alpha will be split based on the ratio of the originally assigned alpha split. For example if the original alpha allocation was split 1/3 for each analysis time point then the recycled alpha would also be split 1/3 across each analysis time point. For example, at the first interim analysis, assume IDFS is statistically significant and the secondary endpoint OS is also statistically significant. The significance level for testing DDFS is therefore $0.005 + (\text{alpha assigned to OS recycled to DDFS and split across the planned analyses})$, i.e. $0.005 + (1\% * 0.005/0.04 = 0.00125) = 0.00625$, or alternatively thought of as $0.005 * 5/4$.

Secondary endpoints will be assessed based on the ITT population. [Table 15](#) shows the different 2-sided significance levels that will be applied to the primary and secondary endpoints across the planned analyses as well as the total alpha spend for each endpoint. Note the significance level for the final analyses of each endpoint will be calculated using the relevant correlation based on the actual number of events for each analysis, the previous alpha spend and the total allocated alpha for that endpoint.

Table 15 Summary of 2-sided significance levels and total alpha spend across the endpoints and analyses

Endpoints	Interim analysis	Final IDFS analysis	DDFS and OS analysis	Final OS analysis	
Estimated timings from FSI**	5.3 years	6.5 years	10 years	14 years	
	Significance level	Significance level	Significance level	Significance level	Total alpha spend (2-sided)
IDFS	0.005	TBC*	N/A	N/A	5%
If IDFS is statistically significant and alpha is not recycled between secondary endpoints at the analysis					
DDFS	0.005	0.02	TBC*	N/A	4%
OS	0.002	0.003	0.004	TBC*	1%
If IDFS is statistically significant and alpha is recycled between secondary endpoints at the analysis					
DDFS	0.00625	0.025	TBC*	N/A	5%
OS	0.01	0.015	0.02	TBC*	5%

*TBC: to be calculated; significance level to be calculated once relevant correlation based on the actual number of events for each analysis is known taking account of previous alpha spend and total allocated alpha

**FSI: first subject in

The IDMC will review the data from the interim analysis. The boundaries defined by the interim p-values for efficacy will be used as guidelines by the IDMC along with all other relevant trial information, including the safety data, to decide if it is appropriate to make a recommendation other than that to continue the trial as planned.

At the time of the interim analysis for superiority, an assessment of futility will also be performed. This futility assessment will be based on the probability of eventually showing statistical significance for the primary endpoint when the final number of IDFS events (n=330) is reached ([Lachin 2005](#)). The determination of this probability will be conditional on the observed data in the ITT population at the time of the interim analysis for superiority and on the assumed hazard ratio for the alternative hypothesis (IDFS HR=0.7). If the probability is less than 0.1, the IDMC will consider the option of declaring futility.

Full details on the process around the interim analysis and the efficacy criteria will be documented in the SAP and IDMC charter.

